6.3 Immediate Reporting of Adverse Events to the Sponsor and to Merck

6.3.1 Serious Adverse Events

A serious adverse event is any adverse event occurring at any dose or during any use of Merck or Amgen products that:

- Results in death;
- Is life threatening;
- Results in persistent or significant disability/incapacity;
- Results in or prolongs an existing inpatient hospitalization;
- Is a congenital anomaly/birth defect;
- Is another important medical event

- **Note:** In addition to the above criteria, adverse events meeting either of the below criteria, although not serious per ICH definition, are reportable to the Sponsor, Merck and Amgen in the same timeframe as SAEs to meet certain local requirements. Therefore, these events are considered serious by Merck and Amgen for collection purposes.
 - Is a new cancer (that is not a condition of the study);
 - Is associated with an overdose.

For the time period beginning when the consent form is signed until the participant presents for cycle 1 day 1, any serious adverse event that occurs to any participant must be reported within 24 hours to the IND holder and within 2 working days to Merck Global Safety and Amgen ONLY if it causes the participant to be excluded from the trial, or is the result of a protocol-specified intervention, including but not limited to washout or discontinuation of usual therapy, diet, placebo treatment or a procedure.

Any serious adverse event, or follow up to a serious adverse event, including death due to any cause other than progression of the cancer under study that occurs to any participant from the time the participant presents for Cycle 1 Day 1 through 90 days following cessation of treatment, or the initiation of new anti-cancer therapy, whichever is earlier, whether or not related to Merck or Amgen product, must be reported within 24 hours to the Sponsor and within 2 working days to Merck Global Safety and Amgen. Additionally, any serious adverse event, considered by an investigator who is a qualified physician to be related to Merck product that is brought to the attention of the investigator at any time following consent through the end of the specified safety follow-up period specified in the paragraph above, or at any time outside of the time period specified in the previous paragraph also must be reported immediately to the IND holder and to Merck Global Safety.

All participants with serious adverse events must be followed up for outcome.

[REDACTED]

A copy of all 15 Day Reports and Annual Progress Reports is submitted as required by FDA, European Union (EU), Pharmaceutical and Medical Devices agency (PMDA) or other local regulators. Investigators will cross reference this submission according to local regulations to the Merck Investigational Compound Number (IND, CSA, etc.) at the time of submission. Additionally, investigators will submit a copy of these reports to Merck & Co., Inc. (Attn: Worldwide Product Safety; [REDACTED] and Amgen (Attn: Global Safety - [REDACTED] [REDACTED] at the time of submission to FDA.

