1.2 Primary Objectives

- Part 1: To determine the safety, tolerability, and RP2D for trebananib when given with pembrolizumab in patients with metastatic solid tumor.
- Part 2 (expansion cohort): To determine the safety and tolerability of the RP2D of trebananib, determined in Part 1, when given with pembrolizumab in patients

with unresectable stage III or stage IV melanoma, metastatic renal cell, ovarian, or colorectal cancer.

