2.3.2.2 Rationale Trebananib Dose Selection

The safety, pharmacokinetics, and antitumor activity of Trebananib were evaluated in Phase I study in patients with advanced solid tumors. Thirty-two patients received weekly intravenous trebananib doses of 0.3, 1, 3, 10, or 30 mg/kg in sequential cohorts. One DLT was reported in the 30 mg/kg cohort (respiratory arrest), which likely was caused by tumor burden that was possibly related to trebananib. The most common toxicities were fatigue and peripheral edema. Proteinuria (n = 11) was observed without clinical sequelae. Only four patients (12%) experienced treatment-related toxicities greater than grade 1. A maximum-tolerated dose was not reached. PK was dose-linear and the mean terminal-phase elimination half-life values ranged from 3.1 to 6.3 days. Serum trebananib levels appeared to reach steady-state after four weekly doses, and there was minimal accumulation. No anti-trebananib neutralizing antibodies were detected (Herbst, Hong et al. 2009). The safety of trebananib was also evaluated in a Phase I study in the Japanese population using dose escalation of 3, 10, or 30 mg/kg. Trebananib was well tolerated at all dose levels and no DLT was observed (Doi, Ohtsu et al. 2012). Trebananib has been evaluated as monotherapy and in combination with chemotherapy or other biologic agents across tumor types, including mixed solid tumors, ovarian, breast, renal, gastric, hepatic, and colorectal cancers. As of the study-specific data cutoff dates, 3611 participants have been enrolled into 20 studies in the trebananib clinical program, of whom 3561 participants have received ≥ 1 dose of trebananib or trebananib placebo, at doses ranging from 0.3 mg/kg to 30 mg/kg intravenously (IV) once weekly (QW). No maximum tolerated dose for trebananib monotherapy has been identified at doses up to 30 mg/kg IV QW. Most of early phase 1b/2 studies (in combination with other agents) were conducted with 3 and 10 mg/kg every week (QW) doses. Later, based on exposure response modeling the 15 mg/kg QW dose was elected in all 3 of the large Phase 3 trials and this dose was explored further in a few Phase 1b/2. Few small studies using 30 mg/kg QW in combination with chemotherapy or other agents are currently ongoing and there is no controlled studies comparing 15 to 30 mg/kg.

A summary of anticipated overlapping toxicities with pembrolizumab includes:

- Diarrhea
- Fatigue
- Nausea and vomiting
- Shortness of breath
- Skin itching
- Rash

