Hypertension: Hypertension (HTN) should be managed per institutional standards and appropriate medical guidelines. trebananib should be held for systolic BP > 200 mmHg or diastolic BP > 110 mmHg, or symptomatic hypertension. trebananib may be resumed at the pre-hold dose upon resolution of symptomatic HTN, systolic BP ≤ 140 mmHg and diastolic BP ≤ 90 mmHg, or returned to participant's baseline blood pressure. If the participant's BP is elevated upon first reading, measurements should be confirmed with a repeat measurement.

For any grade of hypertensive crisis or hypertensive encephalopathy, permanently discontinue trebananib.

Hypokalemia: Participants should have their serum potassium checked as outlined in the Section 9 and managed per institutional guidelines. If hypokalemia is present, replacement should be managed with either oral and/or parenteral replacement, according to institutional practice and to the degree of hypokalemia present. It is recommended that the participant's serum potassium level should be maintained within the normal range, as much as possible, during study treatment. Isolated hypokalemia without clinical sequelae should not be reported as an adverse event.

Pleural Effusion and Ascites: Pleural effusion and ascites should be graded according to CTCAE v4.0. However, since trebananib is known to cause or worsen pre-existing pleural effusions and ascites, these adverse events should be managed as noted below:

Life-threatening pleural effusions or ascites:

- Institute emergency measures per institutional guidelines
- Permanently discontinue trebananib

For all non-life-threatening pleural effusion or ascites:

- Treat per institutional guidelines which may include,

- o non-investigational diuretics,
- o thoracentesis, chest tube drainage or paracentesis
- o pleurodesis
- Investigators should document each paracentesis and /or thoracentesis that occurs while a participant is on study.

Additional toxicities to permanently discontinue trebananib for:

- Gastrointestinal perforation
- Compromised wound healing
- Fistula formation
- Nephrotic syndrome or thrombotic microangiopathy (TMA)
- Reversible posterior leukoencephalopathy syndrome (RPLS)
- Ascites or pleural effusion requiring therapeutic intervention

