5.7 Trial Blinding/Masking

This is an open-label trial; therefore, the Sponsor, investigators, and participant will know the treatment administered.

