6. ADVERSE EVENTS: LIST AND REPORTING REQUIREMENTS

An adverse event is defined as any untoward medical occurrence in a patient or clinical investigation participant administered a pharmaceutical product and which does not necessarily have to have a causal relationship with this treatment. An adverse event can therefore be any unfavorable and unintended sign (including an abnormal laboratory finding, for example), symptom, or disease temporally associated with the use of a medicinal product or protocol-specified procedure, whether or not considered related to the medicinal product or protocol-specified procedure. Any worsening (i.e., any clinically significant adverse change in frequency and/or intensity) of a preexisting condition that is temporally associated with the use of the Merck's product, is also an adverse event.

Changes resulting from normal growth and development that do not vary significantly in frequency or severity from expected levels are not to be considered adverse events. Examples of this may include, but are not limited to, teething, typical crying in infants and children and onset of menses or menopause occurring at a physiologically appropriate time.

Merck and Amgen products includes any pharmaceutical product, biological product, device, diagnostic agent or protocol-specified procedure, whether investigational (including placebo or active comparator medication) or marketed, manufactured by, licensed by, provided by or distributed by Merck and Amgen for human use.

Adverse events may occur during the course of the use of Merck or Amgen product in clinical trials, or as prescribed in clinical practice, from overdose (whether accidental or intentional), from abuse and from withdrawal.

Progression of the cancer under study is not considered an adverse event.

All adverse events that occur after the consent form is signed but before presenting for cycle 1 day 1 must be reported by the investigator ONLY if they cause the participant to be excluded from the trial, or are the result of a protocol-specified intervention, including but not limited to washout or discontinuation of usual therapy, diet, placebo treatment or a procedure.

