14.7 Safety Analysis

Safety data will be presented for all patients who receive at least one dose of either of the study drugs. All adverse events recorded during the trial will be summarized and presented by disease cohort or dose level. The incidence of events that are new or worsening from the time of first dose of treatment will be summarized by dose level or disease cohort, system organ class and/or preferred term, severity (based on CTCAE V4 grade), type of adverse event, and relation to study treatment. Deaths reportable as SAEs and non-fatal serious adverse events will be listed by patient and tabulated by primary system organ class, and type of adverse event.

Safety data from the expansion cohorts will be used to further characterize the safety profile of the drug combination and evaluate the toxicity of the MTD from the dose escalation. We assume that toxicities will be similar for each of the expansion cohorts; however, we will summarize safety data in both the aggregate and by cohort to allow for different adverse event types. Late toxicities observed and assessed as treatment related in the expansion cohort will be monitored. If two or more are observed, enrollment in the expansion cohort will be halted for further review and changing the RP2D will be considered. Given that trebananib is limited in use during only the first 12 weeks (4 cycles), we anticipate there is less chance that the combination of trebananib plus pembrolizumab will exhibit late toxicity in comparison to pembrolizumab given alone.

The following table summarizes the probability of observing at least one patient with a treatment-related toxicity for varying true, but unknown, incidence rates. Estimates in the table are based on individual expansion cohorts of size 12, and also for all 48 patients treated at the MTD.

Underlying incidence rate of treatment-related toxicity	Probability of 1 or more of 12 with treatment-related toxicity	Probability of 1 or more of 48 with treatment-related toxicity
0.01	0.11	0.38
0.05	0.46	0.91
0.10	0.72	0.99
0.15	0.86	>0.99
0.20	0.93	>0.99
0.25	0.97	>0.99

For each expansion cohort of size 12, the probability of observing at least one patient with a dose-related toxicity is greater than 0.70 if the incidence rate of that toxicity is 0.10 or higher. For the aggregated safety data, there is greater than 0.90 probability of observing a toxicity if the incidence rate is 0.05 or higher.

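### Section 14.7 lists only SAE-reportable deaths, so a drug-contributed death ascribed to progression would drop out of the safety death listing, though not out of overall survival or the AE tables

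*Combined protocol and SAP*

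**What the plan says.** Section 6 states: "Progression of the cancer under study is not considered an adverse event". Section 6.3.1 sets the SAE reporting duty from cycle 1 day 1 to 90 days after treatment ends, or to new anti-cancer therapy if earlier, "including death due to any cause other than progression of the cancer under study". Section 6.3.6 repeats the exemption for progression and lifts it when there is evidence of a causal relationship with the drug. It also has the IND holder monitor endpoint and safety data together, and forwards as SAEs any events found on review not to be progression.

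Section 14.7 carries the reporting rule into the analysis: "Deaths reportable as SAEs and non-fatal serious adverse events will be listed by patient". No other safety listing of deaths is planned.

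The Part 2 primary objective in Section 1.2 begins: "To determine the safety and tolerability of the RP2D of trebananib". The study summary gives no control group, and Section 5.7 says: "This is an open-label trial; therefore, the Sponsor, investigators, and participant will know the treatment administered".

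**The concern.** An exemption that makes sense for expedited reporting, where progression events would swamp the system, has become the filter for the final listing of deaths. In a single-arm trial whose primary aim is safety, no control arm can show an excess of deaths. The death listing is where a reader would look for fatal toxicity, and it admits a death only after someone has decided that it was not the cancer, or that the drug may have caused it. Nothing requires that progression by RECIST was documented before a death is ascribed to it.

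That decision can be hard with this drug. Section 5.3.3.2 says that "trebananib is known to cause or worsen pre-existing pleural effusions and ascites", and these findings are also common signs of advancing cancer in the abdomen and chest. At stake is whether the listing can show a fatal contribution from the drug when the first judgement pointed to the tumor.

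**Working it through.** **1. The chain of rules.** Progression is not an AE (Section 6). Death from progression is outside SAE reporting (6.3.1, 6.3.6). Only deaths reportable as SAEs are listed (14.7). So a death ascribed to progression, without recognized evidence of drug causality, is not listed. Overall survival in 14.5 counts it, but without cause or relation to dosing. The 14.7 AE tables show recorded preceding events, but do not link them to the death.

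**2. Timing.** Trebananib is given on days 1, 8 and 15 of four 21-day cycles. The last planned dose is on day 3 × 21 + 15 = 78. Scans are every 12 weeks, 84 ± 7 days, so the first scheduled post-baseline scan falls on about days 77 to 91. Virtually the whole trebananib course precedes it. Unless an unscheduled or end-of-treatment scan was done, a patient who dies during induction will often have no RECIST assessment after baseline.

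**3. Reach of the safeguards.**
- The 6.3.6 review states no criteria and no independent reviewer. Its causality exception turns on the same uncertain judgement.
- The DSMC information in 13.2 is permissive, and its death summary covers 30 days, against the 90-day SAE window.
- The cytology rule in 11.1.3 applies to new or worsening effusions only when measurable tumor has met response or stable disease. That normally cannot be shown before the first post-baseline scan.

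**4. The plan's own safety figure.** The 14.7 table is 1 − (1 − p)^n. For n = 12 and p = 0.01, 0.05, 0.10, 0.15, 0.20 and 0.25 this gives 0.114, 0.460, 0.718, 0.858, 0.931 and 0.968. For n = 48 it gives 0.383, 0.915, 0.994 and then more than 0.999. All twelve cells reproduce.

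**5. Illustration only.** Let p be the true rate of drug-contributed death and m the share of those deaths finally ascribed to progression. The documents give neither; the values below are assumptions. The chance that at least one such death is listed among the 53 expansion patients (12 + 37 + 4) is 1 − (1 − p(1 − m))^53:

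| p | m = 0 | m = 25% | m = 50% | m = 75% |
|---|---|---|---|---|
| 1% | 0.41 | 0.33 | 0.23 | 0.12 |
| 2% | 0.66 | 0.55 | 0.41 | 0.23 |
| 5% | 0.93 | 0.87 | 0.74 | 0.49 |

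**6. One death more or less.** I use an exact two-sided 90% interval, the level that 14.6 sets for response rate; 14.7 plans no interval for deaths. For 0 of 53 the upper limit is 1 − 0.05^(1/53) = 5.5%. For 1 of 53 (1.9%) it solves (1 − p)^53 + 53p(1 − p)^52 = 0.05, which gives 8.6%.

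**The case against.** The strongest reply is that the death listing is one output among several. All AEs are collected from cycle 1 day 1 to 30 days after treatment and tabulated by term, severity and relation. The exemption covers only an event that is itself progression. A serious perforation, hemorrhage or effusion is reportable in its own right, whether or not judged related, even if the later death is put down to cancer. Section 6.3.6 has a route back for reclassified events. Section 11.1.4.3 asks that decline without objective progression be recorded as symptomatic deterioration, with every effort to document progression. Overall survival counts every death.

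Most of this stands. A reader might infer that a toxic death disappears from the primary safety analysis altogether; the documents do not support that. What the reply does not restore is the death itself in the safety listing: grade 5 is recorded only if the death is judged related to an AE, and overall survival carries no cause.

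A reader might also take the earlier single-agent case in Section 2.3.2.2 as a hidden drug death: "One DLT was reported in the 30 mg/kg cohort (respiratory arrest), which likely was caused by tumor burden that was possibly related to trebananib". It shows that attribution can be mixed at this dose. But the event was counted as a DLT despite the tumor explanation, and the text does not say that it was fatal.

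Finally, the stated trebananib half-life is 3.1 to 6.3 days and pembrolizumab may continue for up to two years. For deaths long after induction, resemblance between trebananib toxicity and progression explains little.

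**Conclusion.** The point holds as a cheap improvement to the analysis plan, not as an error of arithmetic or a contradiction. The safety death listing depends on attribution, and the existing safeguards narrow that dependence without removing it. It matters most during trebananib induction.

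The size is unknown. A reader might try to derive one from the colorectal medians in 14.2. With exponential survival, 1 − exp(−ln 2 × 2.957/9) = 0.204 and 1 − exp(−ln 2 × 2.957/5) = 0.336 die in 90 days (2.957 months), or 8.1 and 13.5 of 40. These are all deaths, not misattributed ones. The model starts the survival clock at last dose, the 5-month median is a historical control, and the 40 include 3 dose-escalation patients. The documents do not support using them as the size of the problem. The shift from 5.5% to 8.6% shows only what one death is worth in 53 patients; the actual safety set is everyone dosed and includes dose escalation.

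**What to change.** In Section 14.7, replace the restriction to SAE-reportable deaths with wording such as: *All deaths from first dose to 90 days after the last dose of study treatment, regardless of attributed cause and of any new anti-cancer therapy, will be listed by cohort or dose level. The listing will give recorded cause, days since last dose of each drug, start of any new anti-cancer therapy, AEs and SAEs ongoing at death as far as collected, and whether RECIST progression was documented before death. The number of deaths without prior documented progression will be reported.* The tabulation of non-fatal SAEs and the expedited reporting rules stay as they are.

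The listed cause would still be the investigator's. The all-cause list and the added count are what remove the dependence on it.

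The cost is a longer listing. Dates of death, dosing, scans and subsequent therapy are already collected. The study calendar and Section 10.5.3 provide for survival status but show no cause of death, so one case report field may be needed. Section 6 requires non-serious AEs only to day 30, hence the qualifier on ongoing events. When the window is stated, the 30-day (Section 6), 70-day (6.4) and 90-day (6.3.1) safety periods should be reconciled.

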6.3.2 DF/HCC Expedited Reporting Guidelines

Investigative sites within DF/HCC will report AEs directly to the DFCI Office for Human Research Studies (OHRS) per the DFCI IRB reporting policy.

6.3.3 Expedited Reporting to the Food and Drug Administration (FDA)

The IND holder will be responsible for all communications with the FDA. The Overall PI will report to the FDA, regardless of the site of occurrence, any serious adverse event that meets the FDA's criteria for expedited reporting following the reporting requirements and timelines set by the FDA.

6.3.4 Expedited Reporting to Hospital Risk Management

Participating investigators will report to their local Risk Management office any participant safety reports or sentinel events that require reporting according to institutional policy.

6.3.5 Routine Adverse Event Reporting

All Adverse Events **must** be reported in routine study data submissions to the Overall PI on the toxicity case report forms. **AEs reported through expedited processes (e.g., reported to the IRB, FDA, etc.) must also be reported in routine study data submissions.**

6.3.6 Protocol-Specific Exceptions to Serious Adverse Event Reporting

Efficacy endpoints as outlined in this section will not be reported to Merck or Amgen as described in Section 6.3.1- Immediate Reporting of Adverse Events to the IND holder and to Merck and Amgen, unless there is evidence suggesting a causal relationship between the drug and the event. Any such event will be submitted to the IND holder within 24 hours and to Merck Global Safety and Amgen Global Safety within 2 working days either by electronic or paper media.

Specifically, the suspected/actual events covered in this exception include any event that is disease progression of the cancer under study.

The IND holder will monitor unblinded aggregated efficacy endpoint events and safety data to ensure the safety of the participants in the trial. Any suspected endpoint which upon review is not progression of the cancer under study will be forwarded to Merck Global Safety and Amgen

Global Safety as a SAE within 2 working days of determination that the event is not progression of the cancer under study

Hospitalization related to convenience (e.g., transportation issues etc.) will not be considered a SAE.

